Harp's Pharmacy has a successful medication therapy management (MTM) program where pharmacists are provided time for patient-centered activities for patients with diabetes (DM), hypertension (HTN), the 2 leading causes for CKD, and heart failure (HF), the leading cause of death in CKD. Thirty six percent of patients with DM will develop CKD and hypertension can be both a cause and an effect of CKD (5). In this project they will use their MTM infrastructure to add CKD to their program in select pharmacies in the delta. The CKD tools build on and support actions that improve the underlying conditions that are already being addressed. The "CKD: What Your Need to Know" tools will be used with patients with known CKD or 2 of the 3 conditions covered by MTM and randomized into 1 of 3 education arms that offer various levels of support or a control arm.

Using non-nephrology clinicians to expand access to education earlier in their disease progress is essential. This project will inform how various levels of support provided by pharmacists and their staff using nephrology developed tools can effect patient choice allowing comparisons of support time and outcomes. Empowering patients to be proactive partners in their health care, through education and accountability, by choosing both their RRT and performance goals to protect their kidneys is key to improving outcomes. Demonstrating that non-nephrology clinicians can effectively educate and support these patients will provide models that other clinicians can use.

Minorities, especially in rural areas, are less likely to receive most kinds of care including evidence-based practices, home dialysis or transplantation (4,5). Developing patient-centered approaches to care such as this project can reduce disparities.

One-on-one outreach to educate and motivate patients and seek their feedback can strengthen commitment and adherence to medical regimens. Learning what to expect can promote self-management behaviors.

The AR Department of Health (ADH) Southeast (SE) region covers most of the Delta and was selected because it has the poorest outcomes for patients starting RRT. In 2017, new patients were predominately black (61%), less than half had seen a nephrologist prior to starting RRT, only 1.3% had seen a dietitian, most (92.3%) started hemodialysis using a catheter and 2.1% started on home peritoneal dialysis. Only 2.1% had no insurance (9). This data can be tracked annually to track impact.

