The tools being used were developed by a multidisciplinary team of nephrology experts which are limited in the delta. Courses including train the trainer classes for pharmacies and 10 points of Care for CKD for clinicians will be conducted. Collaboration with local providers can both educate and promote community engagement.

Harp pharmacists expressed randomization concerns. They report that many of their MTM subjects have multiple family members or friends enrolled in the study. This could confound randomization into various arms since these subjects are highly likely to compare and contrast the details of their intervention. It was decided that a cluster randomization schedule would be utilized with each cluster self-selecting a leader that would be enrolled in the study and be responsible for education of the other cluster

members. All cluster members will undergo the same testing.

Specific Aims

The primary aim is to assess the effectiveness of pharmacists and their staff to educate CKD and high risk patients evaluating effectiveness through patient choice of RRT in each arm (e.g. home dialysis choice rate). Secondary aims include 1) Identify actions patients are willing to take to protect their kidney function using the CKD Action Plan that contains 10 performance goals based on international CKD guidelines that can slow CKD progression 2). Describe outcomes and methods used by peer leaders to educate cluster members using the same goals. 4) Compare costs (based on pharmacist and pharmacy associate time) with outcomes in each arm.

Study Design and Procedures

This study is a randomized control pilot study using non-nephrology clinicians to educate patients who are at high risk for CKD how to protect their kidneys and be ready for RRT if and when needed by utilizing nephrology developed educational tools.

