pharmacist or physician confirmed blood pressure and AIC, eGFR, hemoglobin. Patient and/or pharmacist initiated CKD conversation and topics including CKD action plan goal progress. The action plan has 1 knowledge goal related to CKD cause, eGFR and trend and 10 performance goals based on international guidelines and best practices including AIC goal of 7 or less, blood pressure goal of less than 140/90, exercise goal of 30 minutes 5 times a week, medications that may need to be avoided (ex: ibuprofen) or may need to be taken (ex: Statin) if you have CKD and DM or over 50 years old), smoking cessation, kidney friendly diet (may need to modify salt, phosphorus and/or protein intake and be edema free [may require monitoring and adjust salt and water intake], home monitoring of blood pressure, blood sugar and weight, weight management and anemia (goal hemoglobin above 10g/dL)

Study Population

High Risk Subjects will be identified from the Harps MTM program or others having multiple known medical problems (CKD, HTN, DM or heart disease). Know Your Kidney Number Posters which will be available statewide by the time the study starts will be posted in the pharmacy. Even though they are not study specific, they provide pertinent CKD information that could motivate subjects to want to learn more about how to protect their kidneys. Study Patient information Sheets will be available for interested parties.

A total of 100 clusters of 1 or more people from familial or peers groups will be enrolled. The actual number of subjects will depend on the volume of clusters with more than 1 person. This would include approximately 1/3 of the Harps MTM subjects that have both DM and HTN.

Inclusion Criteria

- Adults (any gender)>18 years old
- Enrolled in Harp's MTM program
- Has Known CKD or 2 of the 3 conditions covered in MTM (DM, HTN and Heart Failure)
- Not on dialysis

Exclusion Criteria

- unable to read or speak English
- history of significant cognitive dysfunction unless qualified caregiver is the one being educated
- not personally independent or without any social support

Risks and Benefits

A risk to study participants is the potential for loss of confidentiality of study data.

Measures to protect the confidentiality of study data will be implemented as described in the Data Handling and Recordkeeping section below.

Title: Pragmatic Approach to Chronic Kidney Disease Education in the Delta V.6

PI: [name]

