Know workbook, slide sets, CKD action plan, Label reading exercise, Web-based resource list, data collection sheets, pre and post tests and program evaluation. UAMS staff will participate in the initial education of Harps staff and future education, as requested. UAMS will make the 10 points of CKD Care for Primary Care Providers (PCPs) available to both Harps staff and local PCPs, as requested.

Harps oversight staff and UAMS research staff will have monthly web-based or face to face meetings, with additional communication as needed.

Reporting requirements are the same for each site and outlined in the data section above. A central site may be selected by Harps when the sites are selected and serve as a model or mentoring site.

Data Analysis

Study arms will be compared by RRT choice using logistic regression that includes covariates found to differ between the groups. Results will be reported in terms of odds ratios and their 95% confidence intervals. Each group will be compared on the ability to choose a modality by the end of their 2nd or 3rd MTM visit, depending on their study arm and at the end of the study (June 2022) by comparing pre and post testing and program evaluation answers. To ensure balance in patient characteristics across clusters chi-square or Fisher's exact test, as appropriate, will be used to evaluate categorical measures, whereas two-sample t-test or Wilcoxon rank test, as appropriate, will be used for continuous measures.

The primary study aim is the ability of the participants to choose a dialysis modality by the end of their second or third visit, depending on their study arm. Descriptive statistics will be used to examine the trend in the patients' ability to choose a dialysis modality, level of interest in kidney transplant, the selection of a possible donor and having enough information to decide across the two assessment periods.

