Home dialysis (HOD) is underutilized in management of End Stage Renal Disease (ESRD) and there is a near universal agreement amongst nephrologists and professional societies for improving its rates with a target of around 30-40% of the prevalent ESRD population. Patients, when provided with comprehensive early CKD education, have repeatedly indicated their preferences at similar rates (around 30-40%) for HOD. Despite these findings, the rates of HOD are on the decline. The ADH SE region's HOD rate for incident ESRD patients is less than 3%, AR rate is 11%, the national rate in 10% and the pilot study using the CKD: What you Need to Know rate was 44% for the 68 subjects needing to start RRT by the end of the study and an addition 3 % were able to get pre-emptive transplants.

It is likely that the lack of patient awareness and education play a critical role in the low incident HOD rates. The factors that contribute to this lack of patient awareness and education include the fact that comprehensive

education programs require time- and resource consuming processes, needs multidisciplinary expertise, and are only partially compensated by the current reimbursement standards in the nation. Hence, only limited medical universities and few nephrology practices provide these programs. With over 300,000 Arkansans unaware they have CKD and close to 50,000 more having CKD but little access to proper education, expanding the pool of clinicians and sites that can deliver comprehensive nephrology developed patient education to a larger patient population over a wider geographical area in a cost effective manner has the potential to improve patient outcomes and save health care dollars. It is estimated that HOD saves as much as \$19,000 per patient per year compared to in-center hemodialysis (). Demonstrating that non-nephrology clinicians can effectively educate and support these patients will provide models that other clinicians can use. Increased access to local CKD patient education can improve outcomes for minorities, especially in rural areas, who are less likely to receive most kinds of care including evidence-based practices, home dialysis or transplantation. Developing patient-centered approaches to care, such as this project, can reduce disparities.

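### Known CKD at intake should be a fixed term in the primary model, with modality choice by arm also reported by CKD status; the plan specifies neither

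*Combined protocol and SAP*

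**What the plan says.** **Who enters.** Under Inclusion Criteria, a patient qualifies who "Has Known CKD or 2 of the 3 conditions covered in MTM (DM, HTN and Heart Failure". No eGFR or CKD stage is required. The mix is deliberate: Specific Aims states that the study will "assess the effectiveness of pharmacists and their staff to educate CKD and high risk patients".

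**What is measured.** Data Analysis gives the primary aim as "the ability of the participants to choose a dialysis modality by the end of their second or third visit". This is a stated choice, asked of every participant, and not treatment actually started.

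**How it is analysed.** Data Analysis says: "Study arms will be compared by RRT choice using logistic regression that includes covariates found to differ between the groups". Results are to be odds ratios with 95% confidence intervals. The same section lists control variables, including age, gender, baseline intent to start home dialysis and nephrologist follow-up. History of CKD is not named there, although Study Design and Procedures lists it, with patient-reported eGFR, among the enrollment data. Nothing in the document stratifies randomization by CKD status or plans a CKD interaction, subgroup or separate table.

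**What surrounds it.** Data Analysis also cites home-dialysis rates among incident ESRD patients (under 3% regionally, 11% in the state, 10% nationally) and a pilot whose "rate was 44% for the 68 subjects needing to start RRT by the end of the study".

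**The concern.** Someone already told that they have CKD and someone with diabetes and hypertension alone may answer a question about dialysis modality quite differently. CKD status is therefore a plausible strong predictor of the primary outcome. Two consequences follow.

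1. **Adjustment is left to chance.** Under the planned rule, known CKD enters the model only if the arms happen to differ on it. With roughly a third of 100 clusters per arm, a balance test has little ability to detect an imbalance that matters. The rule also leaves open which odds ratio will be reported. For a predictive covariate, the odds ratio with the term in the model and the one without it are different quantities even under perfect balance, because odds ratios are non-collapsible.
2. **The result cannot be located.** The rationale is to prepare people for RRT, yet the plan does not say how the result will be read for those with known CKD as against those at risk only. If this is decided after the data are seen, any split by CKD status becomes a post hoc choice.

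**Working it through.** **The plan's own figure.** Study Population gives 100 clusters. Data Analysis says that the size came from time and funding, with power secondary. No effect size, intracluster correlation, cluster size or allocation ratio is given, so there is no calculation to reproduce.

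**Inputs**
- Arms: 3, as in the visit schedule. The text elsewhere also mentions 4 arms; 3 is assumed here.
- Subjects per arm: 100/3, about 33, assuming equal allocation, one subject per cluster and no design effect.
- Share with known CKD, *f*: not in the documents. The background's statement "Thirty six percent of patients with DM will develop CKD" concerns lifetime development among diabetic patients. It is not the share of enrollees with known CKD at intake, so *f* is varied.

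**Step 1: what the pooled contrast can distinguish.** Let *d*₁ be the effect in known CKD and *d*₀ the effect in risk-only subjects, both as risk differences. Then

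pooled difference = *f*·*d*₁ + (1 − *f*)·*d*₀.

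This is one equation in two unknowns. At *f* = 0.5, an effect *d* only in known CKD and the same effect only in risk-only subjects both give *d*/2.

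The same holds on the odds-ratio scale. Take 10% and 44% as placeholder rates only. They are not predictions for this trial.
- Effect only in known CKD: education-arm rate = 0.5 × 0.44 + 0.5 × 0.10 = 0.27.
- Effect only in risk-only subjects: education-arm rate = 0.5 × 0.10 + 0.5 × 0.44 = 0.27.
- Pooled odds ratio in both cases: (0.27/0.73)/(0.10/0.90) = 3.33.
- Odds ratio in the group that responds: (0.44/0.56)/(0.10/0.90) = 7.07. In the other group it is 1.

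Adding a fixed CKD term does not separate these cases. Only results by group, or an interaction, can do so.

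**Step 2: how precise a table by CKD status would be.** For *m* subjects per arm in a group, the 95% half-width for a difference between two arms is

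1.96 × √[*p*₁(1 − *p*₁)/*m* + *p*₂(1 − *p*₂)/*m*].

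Two assumptions about the rates give a range: the placeholders 10% and 44%, and the widest case of 50% in both arms.

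| Group's share of the sample | *m* per arm | 10% v 44% | 50% v 50% |
|---|---|---|---|
| 50% | 33 × 0.50 = 16.5 | 1.96 × √(0.3364/16.5) = ±28 points | 1.96 × √(0.5/16.5) = ±34 points |
| 25% | 33 × 0.25 = 8.25 | 1.96 × √(0.3364/8.25) = ±40 points | 1.96 × √(0.5/8.25) = ±48 points |

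Here 0.3364 = 0.44 × 0.56 + 0.10 × 0.90. The normal approximation is rough at about 8 per arm. Correlation within clusters would widen these intervals for a given number of subjects; extra cluster members would narrow them.

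**The case against.** The strongest reply is that the mix is the stated target. The study sets out to educate CKD and high-risk patients so that they are prepared if RRT is ever needed, and the ability to choose after education does not require imminent dialysis. A randomized pooled contrast is valid for that population. This stands.

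The control-variable list is also open-ended. It names nephrologist follow-up and baseline home-dialysis intent, and it refers to outcomes that include eGFR. This stands in part: those are partial markers of CKD, but the list does not say that any of them will be in the primary model whatever the balance.

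Known CKD is also an imperfect marker of nearness to the decision. Entry has no stage threshold, so early CKD counts as known CKD. Data Analysis says that over 300,000 Arkansans are unaware they have CKD, so the group without known CKD may include undiagnosed cases. This stands as a limit on interpretation, but does not remove the case for using a variable already collected.

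Two stronger readings are tempting, and the documents support neither.
- A reader might infer that the trial cannot show whether education works in those who may face the choice. History of CKD and eGFR are collected, so results by CKD status can be produced. What is missing is the plan to do so.
- A reader might infer that the result will be judged against actual RRT-start rates. The planned comparison is between randomized arms. The cited rates serve as rationale, although they sit under Data Analysis. The background remark "This data can be tracked annually to track impact" is attached to no endpoint or analysis.

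**Conclusion.** The concern holds in a limited form. The pooled comparison is valid for the declared mixed population. The plan nevertheless leaves adjustment for known CKD to chance imbalance and plans no result by CKD status, so its single odds ratio cannot say whether an effect lies in known-CKD subjects, risk-only subjects or both. These conclusions follow from the text and the algebra and need no assumed effect.

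The documents do not allow the consequence to be sized. They give neither the enrolled share with known CKD nor expected choice rates in either group, nor a rate of RRT starts among enrollees. A claim that almost no enrollee will start RRT, or that pooling dilutes the effect by a particular amount, would rest on assumptions from outside the plan. The only figures offered here concern precision: about ±28 to ±34 points for a group forming half the sample and ±40 to ±48 for a quarter, assuming 33 subjects per arm and no clustering. Results by group would therefore be descriptive.

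**What to change.** - In Data Analysis, name known CKD at intake as a fixed term in the primary logistic regression, included regardless of observed balance.
- Add a table of modality choice by arm within the known-CKD and no-known-CKD groups, with 95% confidence intervals, labelled descriptive. An arm-by-CKD interaction may be shown as exploratory.
- As a minor clarification, state that the cited rates (under 3%, 10%, 11%, and 44% of 68) concern people starting or needing RRT, and are context and not benchmarks for a stated choice.

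The cost is wording in the analysis section, one model parameter and one table; no new data are needed. The downside is wide intervals in the smaller group. The report should also say that no known CKD does not mean no CKD.

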Harp's pharmacists will screen patients in their MTM program and enroll them in familial or peer clusters consisting of 1 or more subjects and randomize them into 1 of the 4 study arms using a site specific randomization schedule. Each arm will receive pre and post testing and health literacy evaluation. Two education arms will use the 139 page CKD: What You Need to Know workbook including the CKD Action Plan as self-study tools and follow-up during regular MTM appointment. The 3 arms include 2 education arms and a control arm with various levels of intervention: Arm 1) case management model including pharmacist initiated discussion of workbook content and action plan reinforcement, Arm 2) brief introduction of the workbook and action plan reinforcement, Arm and Arm 3) the control group will receive a list of web-based CKD sites and a copy of the action plan with no additional intervention. Patient initiated CKD discussions will be tracked by both the pharmacist and staff by topic and time spent. Time spent by the pharmacist and staff will be calculated along with outcomes and compared in each group. Data collected upon enrollment will include year of birth, race, gender, county of residence, history of CKD, diabetes, hypertension and/or heart failure, patient reported blood pressure, AIC, eGFR and hemoglobin, smoking history, renal transplant history and if is under the care of or has been seen by a nephrologist in the past.

The CKD: What You Need to Know Workbook is 139 pages and includes:

- An Introduction
- 8 Chapters plus resources:
 1. Kidneys and Chronic Kidney Disease (CKD)
 2. Protecting Your kidneys and Slowing CKD Progression
 3. Your Choices for Dialysis and Transplantation
 4. Lab Results: What they mean & What you can control
 5. Chronic Kidney Disease & Eating Habits

6. Chronic Kidney Disease & Meds
7. Learning to Cope with Kidney Disease
8. Paying for Your CKD Treatment
9. CKD Action Plan
10. Web-based Resources
11. Kidney Talk: What do these words mean?
12. Resources

Each section ends with “Frequently Asked Questions”, “Test Your Knowledge” and has space for notes. Patient testimonies are found at the back of 6 chapters.

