Potential benefits include the education received can motivate changes that can protect their kidney function, slow CKD progression and empower them to become more active in their health care.

Ongoing monitoring of international guidelines will be done to ensure education goals remain current.

Data Handling and Recordkeeping

All data received from Harps will be de-identified prior to being sent to UAMS. UAMS study tools will be de-identified. At randomization, the subject will receive a study number including: Harps site #, enrollment #, study arm #, subject initials, and # of people in cluster. In clusters with more than 1 person, the leader will be 1, the 2nd person will be 2, the 3rd 3. The cluster members initials will not be used, they will link to the leader.

Example the first cluster in the study consists of 2 people at site 3 lead by John Doe and randomized to study arm 2. The study number would be 3.1.2.JD.1 for the leader and 3.1.2.JD.2 for the 2nd person.

Data sent to UAMS Research Team. Data can be submitted in REDCap or on Paper.

After Visit 1	Intake Sheet including that includes demographics and medical history, Pre-Test, List of Meds	
After Final Visit	Data Collection Sheet 1, Post-test, Program Evaluation & List of Meds	

EOS: death, start of dialysis or transplantation.

Data will be stored in the UAMS Research office with access limited to study personnel only. UAMS-maintained computers and servers will be used to maintain databased information.

The Principal Investigator will carefully monitor study procedures to protect the safety of research subjects, the quality of the data and the integrity of the study.

At the conclusion of the study, the data will be maintained and later destroyed in accordance with UAMS policy which is for seven years after final reporting or publication of a project, or longer if required by a sponsor or regulation. Any data from subjects who opt out will not be kept for future use.

Multisite Research

Harps district director and research coordinator will be responsible for the education and oversite of each of their sites and not be responsible to UAMS IRB oversight. UAMS will supply the educational tools for both pharmacist, their staff and study subjects. This will include the CKD: What You Need to

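### The primary logistic regression does not say whether it uses cluster leaders only or all tested members; if all, its 95% CIs make no provision for within-cluster correlation

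*Combined protocol and SAP*

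**What the plan says.** The paragraph on randomisation concerns, just before Specific Aims, adopts cluster randomisation "with each cluster self-selecting a leader that would be enrolled in the study and be responsible for education of the other cluster" members. It adds: "All cluster members will undergo the same testing". Study Design and Procedures has the pharmacists "enroll them in familial or peer clusters consisting of 1 or more subjects" and randomise them to an arm. Study Population sets the total at 100 clusters and states: "The actual number of subjects will depend on the volume of clusters with more than 1 person".

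The primary aim in Specific Aims reads: "The primary aim is to assess the effectiveness of pharmacists and their staff to educate CKD and high risk patients", judged through choice of renal replacement therapy (RRT). A separate secondary aim is to "Describe outcomes and methods used by peer leaders to educate cluster members using the same goals".

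For the primary comparison, Data Analysis states: "Study arms will be compared by RRT choice using logistic regression that includes covariates found to differ between the groups". Results are to be given as odds ratios with 95% confidence intervals. The section refers to participants, patients and groups without saying which cluster members are meant. Nowhere do the documents mention an ICC, design effect, random effect, generalised estimating equations (GEE), robust standard error or cluster-level summary.

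**The concern.** There are two gaps, one certain and one conditional.

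**The analysis set is undefined.** Leaders are taught by pharmacy staff; the other members are, at least in part, taught by their leader. An odds ratio from leaders alone and one from everybody answer different questions, and only the first matches the wording of the primary aim. Left open, the choice could be made after the data are seen.

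**The intervals may be too narrow.** Members of a cluster are relatives or friends, share one teacher and are randomised together. It is reasonable to expect their RRT choices to be positively correlated, although the plan does not say so. A logistic model that treats them as independent overstates the information in the data, and the odds ratio with its interval is how the plan reports this comparison.

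**Working it through.** **Step 1. Which people are in the model?** The text supports both readings.

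- *Leaders only.* The leader is the person described as enrolled. The primary aim concerns teaching by pharmacists and their staff. Members' outcomes have their own descriptive secondary aim, and the sample-size paragraph in Data Analysis presents clusters as a way to train peer educators and describe their methods.
- *All members.* Clusters are enrolled as groups of subjects. Every member is tested, and the subject count grows with multi-person clusters. The sample-size paragraph expects the number of subjects may be well above 100. Data Handling and Recordkeeping numbers each person: "In clusters with more than 1 person, the leader will be 1, the 2nd person will be 2, the 3rd 3".

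Nothing settles it.

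**Step 2. How much would the choice change the analysed group?** Cluster sizes are not given, so these are assumed scenarios for 100 clusters. The share of analysed people who are not leaders would be:

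- a quarter of clusters pairs: 25/125 = 20%
- half pairs: 50/150 = 33%
- all of size 2: 100/200 = 50%
- all of size 3: 200/300 = 67%

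**Step 3. What happens to the interval if all members are analysed as independent?** The plan has no power or error figure to reproduce. With cluster sizes m:

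- design effect DE = 1 + (Σm²/Σm − 1) × ICC
- true coverage of a nominal 95% interval = 2Φ(1.96/√DE) − 1
- widening needed = √DE

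For half pairs, Σm = 150 and Σm² = 50×1 + 50×4 = 250. At ICC 0.3, DE = 1 + (250/150 − 1) × 0.3 = 1.20, so √DE = 1.10 and coverage is 92.6%. For quarter pairs, Σm = 125 and Σm² = 175.

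| Assumed cluster sizes | ICC 0.1 | ICC 0.3 | ICC 0.5 |
|---|---|---|---|
| Leaders only, or all singletons | 95% | 95% | 95% |
| Quarter pairs | 94.5% (×1.02) | 93.6% (×1.06) | 92.6% (×1.10) |
| Half pairs | 94.2% (×1.03) | 92.6% (×1.10) | 91.0% (×1.15) |
| All size 2 | 93.8% (×1.05) | 91.4% (×1.14) | 89.0% (×1.22) |
| All size 3 | 92.6% (×1.10) | 87.9% (×1.26) | 83.4% (×1.41) |

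In terms of information, 200 people in pairs are worth 200/1.1 = 182, 200/1.3 = 154 or 200/1.5 = 133 independent people at the three ICCs.

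**Step 4. Check by simulation.** All runs compared two arms of 33 clusters (100 over the three arms in the visit table) with no true effect.

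- *No covariates, outcome rate 30%, 20,000 runs per setting.* Coverage of ordinary logistic regression at ICC 0.1 / 0.3 / 0.5 was 94.1 / 91.3 / 88.8% for size 2 and 92.8 / 87.7 / 83.3% for size 3. Singletons gave 95.3%.
- *One person-level and one cluster-level covariate, outcome rate 0.5, 10,000 runs per setting.* Log-odds of 0.5 per SD were assumed for each covariate. Coverage at the same ICCs was:

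| Cluster sizes | Ordinary logistic | GEE with small-sample correction |
|---|---|---|
| Half pairs | 94.5 / 92.4 / 91.7% | 96.3 / 96.1 / 96.2% |
| All size 2 | 93.4 / 91.2 / 89.2% | 95.7 / 96.0 / 96.2% |
| All size 3 | 92.7 / 88.3 / 84.0% | 96.0 / 95.8 / 96.2% |

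Singletons with ordinary logistic regression gave 95.0%. Both sets agree with the formula to within about a percentage point.

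**The case against.** The plan says only logistic regression; it does not say that clustering will be ignored, and GEE or a random-intercept model would also fit that description. That is fair. The narrow intervals need four things together: members are analysed, multi-person clusters enrol, choices within them are alike, and the model is fitted without adjustment. But a plan that randomises clusters should not leave the last point to be guessed.

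Leaders only may be the natural reading, since the endpoint is timed by pharmacy visits. Against that, eligibility requires enrolment in the pharmacy's medication therapy management programme, so members may attend visits too. This also blurs the line between staff-taught and peer-taught people. Neither point decides the matter.

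The size of the error rests on assumed values, and the worst figures need every cluster to be of size 3 with a high ICC, which the documents never describe as typical. That stands. With few pairs and a low ICC the error is small, and there the corrected GEE is no better calibrated, only conservative: 96.3% against 94.5% for half pairs at ICC 0.1 in the covariate simulation.

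Finally, this is a pilot sized by feasibility, with power a secondary consideration. That excuses low power; it does not excuse invalid intervals, because between-arm odds ratios with 95% intervals are still planned.

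**Conclusion.** The concern holds. That the primary analysis set is undefined is certain, depends on no assumed number, and matters as soon as one multi-person cluster enrols. The interval error is conditional. If all members are analysed without adjustment, coverage falls from 95% to between 94.5% and 91.0% when a quarter to a half of clusters are pairs, and to between 93.8% and 83.4% when all clusters are of size 2 or 3, for ICCs of 0.1 to 0.5. Cluster sizes and ICC are assumptions throughout, so the documents cannot show which value applies. There is no such error under leaders only or if every cluster is a single person. The plan should be corrected before analysis.

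**What to change.** In Data Analysis:

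1. State the primary analysis set: cluster leaders only, or all tested participants.
2. If the set can contain more than one person per cluster, fit the logistic model with the randomised cluster as the independent unit. The cluster is the study number without its last field. One suitable choice is GEE with an exchangeable working correlation (independence if that fails to converge), small-sample-corrected robust standard errors and a t reference based on the number of clusters. A random-intercept logistic model is an alternative; the text should then say that the odds ratio is cluster-specific.
3. If the set is leaders only, ordinary logistic regression has no family or peer correlation to handle. Member outcomes stay descriptive under the secondary aim, and any interval that pools several members of a cluster is cluster-adjusted. Correlation within pharmacy site is a separate question, not addressed here.

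The cost is wording only, because the study number already codes cluster and leader or member status. With all members and the GEE, simulated intervals widen by a median factor of 1.08 (half pairs, ICC 0.1) to 1.48 (all size 3, ICC 0.5), and coverage is slightly conservative at about 96%. A check with quarter pairs at ICC 0.1 gave about 1.07, where the formula needs 1.02. With leaders only, at most 100 people are analysed and member data add nothing to primary precision.
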